[Protocol for Clinical Trial]

The effects of direct swallowing training and oral sensorimotor stimulation in preterm infants

2015.07

NCT02508571

Table of Contents

1. Title of the Clinical Trial	5
2. Name and Address of the Clinical Trial Institution	5
3. Study Period	5
4. Objectives of the Study	5
5. Study Design	5
6. Study Participants	5
7. Study procedures	7
8. Study evaluation	12
9. Dropout	15
10. References	16

[Clinical Trial Overview]

Clinical Trial Title	The effects of direct swallowing training and oral sensorimotor stimulation in preterm infants
Objective of the Clinical Trial	This study aims to evaluate whether the application of direct swallowing training (DST) and oral sensorimotor stimulation (OSMS) in preterm infants preparing for the transition from tube feeding to oral feeding shortens the time required for complete oral feeding and improves oral feeding skills. Additionally, the study will assess the long-term impact of oral feeding

Protocol_DST and OSMS_oral feeding performance

	interventions in the neonatal intensive care unit (NICU) on developmental outcomes and dietary habits.
Phase of the Clinical Trial	Prospective, blind, controlled, randomized trial
Clinical Trial Institution	Seoul National University Hospital
Principal Investigator	[name], Department of Pediatrics, Seoul National University College of Medicine
Study Design	single-center, prospective, open-label, controlled, randomized study
Study participants	
 -Gestational age at birth < 32+0 weeks -Eligible for respiratory support using heated humidified high-flow nasal cannula (HHFN) or equivalent, within 33+0 weeks -Infants who have been progressing with tube feeding at a volume of 120 ml/kg/day or more -Informed consent obtained from parents or legal guardians
Number of participants	189
Study methodology	
In this study, preterm infants who are receiving adequate tube feeding and have been discontinued from continuous positive airway pressure (CPAP) for at least 48 hours will be divided into three groups:
 
 - Control Group -DST Group (Direct Swallowing Training) -DST + OSMS Group (Direct Swallowing Training + Oral Sensorimotor Stimulation) 
Each group will receive its respective intervention.

Study period	From IRB approval date in 2015 to December 30, 2025.

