6.2 Target sample size and rationale for calculation

The primary objective of this study is to determine whether there is a difference in the time taken to reach full oral feeding, from the initiation of oral feeding, when DST and OSMS are applied to preterm infants preparing for the transition from gavage feeding to oral feeding.

To calculate the sample size required to achieve the research objective, the following assumptions are made:

Protocol_DST and OSMS_oral feeding performance

(1) Level of significance (α): 0.0167 (two-tailed test).

When comparing the control group with the DST group, the control group with the DST + OSMS group, and the DST group with the DST + OSMS group, there is an issue of multiple comparisons. To address this, Bonferroni correction is applied. The significance level used is $0.05/3 = 0.0167$.

(2) Group ratio: Control group : DST group : DST + OSMS group = 1 : 1 : 1.

(3) Type II error (β): 0.20, maintaining a test power of 80%.

(4) Primary outcome: Days from start to full oral feeding (SOF-FOF).

(5) The hypothesis of the study is as follows:

[Hypothesis 1]

Null hypothesis: There is no difference in SOF-FOF days between the control group and the DST group.

Alternative hypothesis: There is a difference in SOF-FOF days between the control group and the DST group.

[Hypothesis 2]

Null hypothesis: There is no difference in SOF-FOF days between the control group and the DST + OSMS group.

Alternative hypothesis: There is a difference in SOF-FOF days between the control group and the DST + OSMS group.

[Hypothesis 3]

Null hypothesis: There is no difference in SOF-FOF days between the DST group and the DST + OSMS group.

Alternative hypothesis: There is a difference in SOF-FOF days between the DST group and the DST + OSMS group.

(6) Sample size calculation method: The PASS program (Power Analysis and Sample Size software; <http://www.ncss.com>) will be used.

Based on existing research data (16, 18), the average SOF-FOF days for each group were assumed as follows: Control group 20.8 days, DST group 14.6 days, and DST + OSMS group 10.0 days. The pooled standard deviation was calculated to be 7.19. With a significance level of 1.67% and a two-tailed test, the required sample size for 80% power is 56 participants per group, for a total of 168 participants.

Protocol_DST and OSMS_oral feeding performance

Assuming a 10% dropout rate, the final sample size, accounting for dropouts, is 189 participants.

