7.2 Randomization

In this study, eligible participants who meet all the inclusion criteria will be randomly assigned in a

Protocol_DST and OSMS_oral feeding performance

1:1:1 ratio to the control group, the DST group, or the DST + OSMS group. However, randomization will be stratified by gestational age and sex.

The randomization will be done using a block randomization method with block sizes of 3 and 6, generated through SAS 9.2. The randomization process will be managed via the MRCC website (<http://mrcc.snu.ac.kr>) using web-based randomization.

The detailed randomization procedure is as follows:

- Study coordinators will be provided with an ID and password for randomization.
- The study coordinators will log in to the MRCC website (<http://mrcc.snu.ac.kr>) and access the randomization screen.
- The study coordinator will enter the participant's basic information, test results, inclusion/exclusion criteria, and other relevant data, and click the confirmation button.
- If the participant is eligible, a randomization number will appear on the screen.
- The randomization screen will be printed, and one copy will be kept for records.
- The study coordinator will use the assigned randomization number to prescribe the corresponding intervention.

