7.3 Intervention protocol

7.3.1. Initiation

The intervention will begin at the point when the preterm infant, who is receiving sufficient feeding via gavage (≥ 120 ml/kg/d), has reached a postmenstrual age (PMA) of at least 28 weeks and has been at least 48 hours since the removal of nasal continuous positive airway pressure (CPAP) therapy.

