8.1 Basic clinical factors

- Gestational age, birth physical measurements, sex, singleton/twin, delivery type, Apgar score, umbilical cord blood gas findings, birth place, pregnancy complications, use of antenatal steroids, presence of pathological chorioamnionitis
- Public insurance status (general insurance vs. social assistance), marital status, parents' education level, parents' age, parents' occupation
- Neonatal respiratory distress syndrome, confirmed sepsis, patent ductus arteriosus (treatment status), abnormal findings on brain ultrasound, necrotizing enterocolitis requiring medical treatment, apnea of prematurity (treatment status), timing of discontinuation of apnea medication, feeding intolerance (treatment status), neonatal rickets, bronchopulmonary dysplasia, duration of mechanical ventilation (invasive, non-invasive, supplemental oxygen)
- Age (postnatal days, postmenstrual age) and physical measurements, feeding volume, and respiratory support methods at the following time points:
 - * When the initial gavage feeding starts,
 - * When the intervention begins,
 - * When the feeding volume reaches 120 ml/kg/d,
 - * When the first oral feeding begins,
 - * When the oral feeding volume reaches 50% and 100% of 120 ml/kg/day,
 - * When all feeding transitions to oral feeding, regardless of feeding-related side effects,
 - * When full oral feeding is possible without any feeding-related side effects that require special treatment (end of intervention),
 - * When full oral feeding is possible without any feeding-related side effects.
- The day of birth weight recovery, duration of TPN, duration of gavage feeding, type of milk, period until resolution of feeding-related apnea, bradycardia, and oxygen saturation decrease after reaching full oral feeding.
- Total hospitalization period, age (in postnatal days, postmenstrual age) and physical measurements at discharge.
- Results of developmental assessment tests for long-term developmental evaluation in eligible patients for clinical purposes:
 - * Bayley Scales of Infant and Toddler Development, 3rd Edition (corrected age 18-24 months)

Protocol_DST and OSMS_oral feeding performance

(Indications: GA < 32 weeks or BW < 1500g)

* Korean version of the McArthur-Bates Communicative Development Inventory (at 36±2 months) (Indications: GA < 32 weeks)

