8.3 Outcome

8.3.1. Primary outcome: The period from the start of oral feeding to the time when full oral feeding is achieved without any feeding-related side effects requiring special treatment.

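### The primary interval starts at first oral feeding, which the intervention could move, so a SOF-FOF difference alone cannot show that infants reached full oral feeding sooner

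*Combined protocol and SAP*

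**What the plan says.** The Clinical Trial Overview asks whether DST and OSMS in "preterm infants preparing for the transition from tube feeding to oral feeding shortens the time required for complete oral feeding". Section 8.3.1 sets the primary outcome as "The period from the start of oral feeding to the time when full oral feeding is achieved", with no side effects of feeding that need special treatment. Section 6.2 sizes the trial on the same interval, SOF-FOF, and words the primary objective as time to full oral feeding counted from the first oral feeds.

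On timing, the inclusion criteria in 6.4.1 require adequate tube feeding, and under 7.2 "eligible participants who meet all the inclusion criteria will be randomly assigned in a" 1:1:1 ratio. Section 7.3.1 states: "The intervention will begin at the point when the preterm infant, who is receiving sufficient feeding via gavage", subject to a minimum postmenstrual age and a period off CPAP. It does not tie the start of the intervention to the first oral feed. Section 8.1 lists the start of the intervention and, as a separate time point, "When the first oral feeding begins".

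Of the secondary outcomes in 8.3.2, the two feeding periods also run from the start of oral feeding. Length of hospital stay does not.

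**The concern.** Randomisation makes the arms comparable at the moment of randomisation. An interval that opens at a later event keeps that protection only if treatment leaves the event alone. DST is swallowing practice given before or during the move to oral feeds (7.3.4.1), so an effect on readiness for the first oral feed is plausible. The documents give no criterion for starting oral feeds and do not say that the decision is made blind to allocation.

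If the start moves, SOF-FOF mixes two effects. A shorter interval may mean that full oral feeding came sooner, or only that oral feeding began later. An unchanged interval may hide a real gain when both ends moved earlier. No listed feeding-time outcome would tell these apart, although the objective in the Overview concerns the time needed to reach complete oral feeding.

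**Working it through.** **Inputs (section 6.2).** Means 20.8, 14.6 and 10.0 days; SD 7.19; two-sided alpha 0.05/3 = 0.0167; 56 per arm; 10% dropout; total 189.

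**The plan's own figure.** The smallest gap is 14.6 − 10.0 = 4.6 days. A two-sample t-test with 80% power needs 53 per arm. Multiplying by π/3, the usual allowance for a Mann-Whitney test, gives 53 × 1.0472 = 55.5, so 56. (Section 8.4.2 lists the Mann-Whitney test; its use for sizing is inferred.) For dropout, 56/0.9 = 62.2, so 63 per arm, and 3 × 63 = 189. The sizing reproduces, so the point concerns the endpoint and not the arithmetic.

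**Effect of a moved start.** SOF-FOF is the date of full oral feeding minus the date of first oral feeding. Between two arms:

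reduction in SOF-FOF = (days by which full oral feeding is earlier) − (days by which first oral feeding is earlier),

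with a later first oral feed counted as negative.

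**Test at the planning values.** Standard error = 7.19 × √(2/56) = 1.359 days. The critical t on 110 df at 0.0167 is 2.430, so an observed gap of 2.430 × 1.359 = 3.30 days is significant. The noncentrality is the net gap divided by 1.359. Probabilities are from the noncentral t distribution.

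| Full oral feeding | First oral feeding (assumed) | Net SOF-FOF gap (days) | Noncentrality | P(significant) |
|---|---|---|---|---|
| 6.2 days earlier | unchanged | 6.2 | 4.56 | 98.3% |
| 6.2 days earlier | 2 days earlier | 4.2 | 3.09 | 74.5% |
| 6.2 days earlier | 3 days earlier | 3.2 | 2.36 | 47.3% |
| unchanged | 1 day later | 1.0 | 0.74 | 4.9% |
| unchanged | 2 days later | 2.0 | 1.47 | 17.4% |
| unchanged | 3 days later | 3.0 | 2.21 | 41.5% |

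The 6.2-day gap is control versus DST (20.8 − 14.6). For DST versus DST + OSMS, power at 4.6 days is 82.8%. It would fall to 30.7% if first oral feeding came 2 days earlier in the combined arm (net 2.6 days). Both of those arms receive DST, so only a shift due to OSMS, or to the combination, would count there.

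**Precision of a clock that starts at randomisation.** The documents give no SD for the wait from randomisation to first oral feeding. If the wait has SD w and is independent of SOF-FOF, the total SD is √(7.19² + w²). For w = 3, 5, 7 this is 7.79, 8.76, 10.03. By normal approximation, power for 4.6 days at 56 per arm goes from 84% (w = 0) to 77%, 65%, 51%. A negative correlation would soften or reverse the loss: with w = 5 and correlation −0.5 the total SD is 6.38 and power is 92%.

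**The case against.** The strongest reply is that SOF-FOF is a deliberate endpoint that matches its own hypotheses. Section 6.2 states the objective as time from first oral feeding, section 4 speaks of the transition period, and the three null hypotheses concern SOF-FOF days. That stands, and it rules out one tempting inference: that the 17% and 42% are inflated type I error. If first oral feeding really moves later in one arm, the SOF-FOF null is false and rejecting it is correct. The fault would lie in describing the result as faster attainment.

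A reader might also infer that unblinded staff decide when oral feeding starts and so can steer the outcome. The documents do not support this. No section says who decides. The Overview calls the trial both blind and open-label, and the section on the blind study provides screens for all interventions and a 15-minute sham for controls. If these work, they limit staff-driven shifts, but they cannot prevent a real effect on readiness.

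Two further replies stand in part. No document shows that first oral feeding will move, by how much, or in which direction; the protocol expects better feeding ability, which if anything suggests an earlier start and so a bias against the intervention. And the order of events is inferred, since no criterion excludes an infant already taking some oral feeds. Sections 6.4.1, 7.2, 7.3.1 and 8.1 together nevertheless point to randomisation and treatment coming first.

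**Conclusion.** The point holds as a limit on interpretation, not as an error in the primary test or the sample size. SOF-FOF validly compares the length of the transition period. It cannot by itself answer the Overview's question of whether full oral feeding is reached sooner, and length of stay is only an indirect check.

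An assumed shift of 2 to 3 days is enough to matter: a 17% to 42% chance of a significant SOF-FOF difference with no change in attainment, or a fall in power from 98% to between 74% and 47% for a 6.2-day gain. These figures rest on the planning SD, 56 per arm, and first oral feeding following randomisation.

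**What to change.** Keep SOF-FOF as the primary outcome. Add to 8.3.2, as supportive outcomes for the same three contrasts, with estimates and confidence intervals (98.33% would match the 0.0167 level):

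- (i) days from randomisation to full oral feeding as defined in 8.3.1;
- (ii) postmenstrual age at full oral feeding;
- (iii) days from randomisation to first oral feeding.

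Add the date of randomisation to the time points in 8.1, which lists the start of the intervention but not randomisation. The printed randomisation screen kept under 7.2 may supply it.

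State that a SOF-FOF difference will be described as faster attainment of full oral feeding only if the estimate and confidence interval for (i) support it, and otherwise only as a shorter transition period. It is not enough that (i) points the same way. In simulations with no change in full oral feeding and first oral feeding 2 or 3 days later (wait SD 3 to 7 days, correlation with SOF-FOF 0 to −0.5, all assumed), about 70% to 99% of the significant SOF-FOF benefits still met that weaker rule. A chance-short SOF-FOF also shortens (i). By contrast, when attainment is equal, a 98.33% interval for (i) excludes zero in either direction only 1.67% of the time.

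The cost is some wording, one added date and a little more analysis; the sample size does not change. Age and postmenstrual age at first and full oral feeding are already collected. The drawback is that (i) is probably less precise than SOF-FOF, so it may leave a real gain unconfirmed.

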8.3.2. Secondary outcomes

- The period from the start of oral feeding to the first achievement of full oral feeding
- The period from the start of oral feeding to the achievement of full oral feeding without any feeding-related side effects
- Overall transfer, proficiency, rate of transfer, volume loss
- length of hospital stay
- NOMAS
- Bayley Scales of Infant and Toddler Development (Bayley-III)
- Korean version of the McArthur-Bates Communicative Development Inventory (K-MBCDI)
- Korean Wechsler Preschool and Primary Scale of Intelligence (K-WPPSI-IV)
- Korean Developmental Screening Test for Infants and Toddlers (K-DST)
- Strengths and Difficulties Questionnaire (SDQ)
- Behavioral Pediatric Feeding Assessment Scale (BPFAS)

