6.4 Inclusion and Exclusion criteria for enrolment

6.4.1. Inclusion criteria

- (1) Preterm infants with a gestational age of less than 32+0 weeks.
- (2) Infants currently receiving sufficient tube feeding (at least 120 ml/kg/day).
- (3) Infants who can be treated with heated, humidified high-flow nasal cannula (HFNC) within 33+0 weeks.
- (4) Infants who only have feeding-related issues remaining, with no need for special medical treatment.
- (5) Infants whose parents voluntarily sign the informed consent form for participation in the study.

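### Length of hospital stay has no stated start point, and the only matching stay item recorded includes time before randomisation, which costs precision unless the analysis allows for it

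*Combined protocol and SAP*

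**What the plan says.** Section 8.3.2 gives the outcome as "length of hospital stay", with no start, end or unit. The feeding-transition outcomes in 8.3.1 and 8.3.2, by contrast, each name their starting event.

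Among the recorded data in section 8.1, the matching entry is "Total hospitalization period, age (in postnatal days, postmenstrual age) and physical measurements at discharge". The same section also plans "Age (postnatal days, postmenstrual age) and physical measurements, feeding volume, and respiratory support methods at the following time points", and one of those time points is "When the intervention begins".

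The entry rules put a variable stretch of hospital time before randomisation. Section 6.4.1 admits "Preterm infants with a gestational age of less than 32+0 weeks", with no lower limit, and requires tube feeding to be established already. Under section 7.3.1 the intervention begins once the infant "has reached a postmenstrual age (PMA) of at least 28 weeks and has been at least 48 hours since the removal" of nasal CPAP.

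Section 7.2 stratifies randomisation by gestational age and sex, and keeps a printed copy of the randomisation screen. Section 8.4.2 assigns two-way and repeated-measures analysis of variance to the primary and secondary outcomes. It names neither the factors nor any covariate for stay.

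**The concern.** If the recorded total is what gets analysed, each infant's value is the sum of two parts: hospital time before randomisation and hospital time after it. Only the second can respond to treatment. The first depends largely on how early the infant was born and how ill it was in the first weeks. It can be short for an infant born just under 32 weeks and long for one born much earlier.

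Stay is one of the secondary outcomes most closely tied to faster oral feeding. If variation fixed before treatment stays in the error term, a real shortening of several days could be reported as no clear difference and then read as no effect on discharge.

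**Working it through.** **The plan's own figure.** There is none for stay. The primary sample size (section 6.2) does reproduce. For a 4.6-day difference (14.6 − 10.0), SD 7.19, two-sided 0.0167 and 80% power, a t-test needs 53 per group. Dividing by the Mann-Whitney efficiency 3/π gives 55.5, so 56. Then 56/0.9 = 62.2, so 63, and 3 × 63 = 189. I use 56 per arm below.

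**What matters is spread, not length.** Adding the same 35 days to every infant leaves the t-test p-value unchanged. Power is lost only because the earlier stay differs between infants.

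**First route: assumed SDs.** None of these inputs is in the documents. I assume an SD of 1.5–2 weeks for gestational age at birth (GA), 1–1.5 weeks for postmenstrual age (PMA) at start, and 1.5–2 weeks for PMA at discharge. The GA–discharge correlation runs from 0 to −0.5 and the start–discharge correlation from 0.3 to 0.5.

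- Total stay = PMA at discharge − GA. Its variance is s_D² + s_G² − 2·r_GD·s_G·s_D.
- Post-start stay = PMA at discharge − PMA at start. Its variance is s_D² + s_S² − 2·r_SD·s_S·s_D.
- Case A (s_G = 2, s_S = 1, s_D = 2, r_GD = −0.5, r_SD = 0.5): total √(4 + 4 + 4) = 3.46 weeks = 24.2 days; post-start √(4 + 1 − 2) = 1.73 weeks = 12.1 days. Variance ratio 4.0.
- Case B (1.5, 1.5, 2, −0.5, 0.3): total √(4 + 2.25 + 3) = 3.04 weeks = 21.3 days; post-start √(4 + 2.25 − 1.8) = 2.11 weeks = 14.8 days. Variance ratio 2.1.

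Over the whole grid, total SD is about 15–24 days, post-start SD about 9–15 days and the variance ratio 1.4–5.3. Total stay was the noisier measure in every combination.

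Power comes from the noncentral t with 110 degrees of freedom and noncentrality (difference/SD) × √(56/2), for 7 days at two-sided 0.05:

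| | SD, days | Noncentrality | Power |
|---|---|---|---|
| A, total | 24 | 1.54 | 33% |
| A, post-start | 12 | 3.09 | 86% |
| B, total | 21.3 | 1.74 | 41% |
| B, post-start | 14.8 | 2.50 | 70% |

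In case A the difference detectable with 80% power is 12.8 days for total stay and 6.4 days for post-start stay. Where total SD is near 15 days, the bottom of the grid, power on total stay is itself about 70%, so the penalty is then mild.

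**Second route: the protocol's own differences.** Section 6.2 implies differences of 6.2, 10.8 and 4.6 days in the primary outcome. Assume that they carry over in full to discharge, that post-start stay has SD 7.19, and that it is independent of the pre-start stay. Then SD of total stay = √(7.19² + SD_pre²). Power with 56 per arm at 0.0167, unadjusted:

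| SD_pre, days | 6.2 days (control v DST) | 10.8 days (control v DST+OSMS) | 4.6 days (DST v DST+OSMS) |
|---|---|---|---|
| 0 (counted from start) | 98% | >99% | 83% |
| 7 | 80% | >99% | 50% |
| 14 | 37% | 88% | 19% |
| 21 | 18% | 56% | 10% |

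For scale, if the start fell at a fixed PMA and GA were uniform from 24, 26 or 28 weeks up to 32, SD_pre would be (range in weeks × 7)/√12 = 16, 12 or 8 days.

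**What adjustment recovers.** Linear adjustment of total stay for GA leaves a residual SD of s_D × √(1 − r_GD²). In both cases that is 2 × √0.75 weeks = 12.1 days. This equals the post-start SD in case A and is below it in case B. Under the second route at SD_pre 16.2 days, removing 75% of the pre-start variance (an assumption) raises power from 29% / 79% / 15% to 73% / >99% / 43%.

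**The case against.** The strongest reply is that the plan can already deal with this. Gestational age is a stratification factor (7.2) and a subgroup variable (8.4.1), and the unnamed second factor in the two-way analysis of variance could be the gestational-age stratum. As shown above, adjusting for gestational age can recover the whole loss without redefining the outcome. That stands as an argument for a second remedy. It does not show that the plan uses it: section 8.4.2 names no factor, a subgroup analysis is not an adjustment, and coarse strata would recover less than gestational age as a continuous variable.

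It is also fair that total stay is a legitimate resource and family measure, that this is one secondary outcome among many, and that all the SDs of stay are assumed. These points limit the severity.

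Four stronger readings are tempting, and the documents do not support them:

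- *The outcome is defined as total stay.* Section 8.3.2 does not say so. It is an inference from the data list in 8.1, which also records the ages needed for a post-start measure.
- *Earlier stay swamps any real effect.* In the second route the 10.8-day contrast keeps 56% to over 99% power at SD_pre of 7–21 days. Even at a total SD of 24 days it has about 66% power at 0.05.
- *The comparison is biased.* Allocation is randomised and stratified by gestational age, a main expected driver of the earlier stay.
- *Stay is miscounted for infants born elsewhere.* Recording place of birth does not show how their stay would be counted, and postnatal age at discharge gives time from birth in any case.

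**Conclusion.** The point holds as a question of definition and precision. The outcome has no start point. The only stay item that matches it includes time the arms cannot affect, and no adjustment is stated.

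Analysed unadjusted, total stay could obscure the smaller contrasts: 33–41% power for a 7-day effect, against 70–86% for post-start stay, in the two worked cases. The largest contrast may still be detectable. The direction is secure, since total stay was noisier throughout the range examined. The size rests on assumed SDs and correlations and on an assumed effect on discharge, and the loss could be small if gestational ages in the sample are narrow. Severity is minor to moderate.

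**What to change.** In section 8.3.2, define the outcome as days from randomisation to discharge, with postmenstrual age at discharge as the supporting measure. In section 8.4.2, state that it is analysed with the gestational-age stratum in the model. Keep total hospitalisation as a reported description, adjusted for gestational age if it is tested.

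The cost is a few lines of text. Ages at intervention start and at discharge are already collected (8.1). The date of randomisation is not among the time points in 8.1, but the randomisation record is retained (7.2); the date should be confirmed as a data item. The one small loss is that total stay, a familiar resource measure, is no longer the version tested.
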